However, existing research pointed out that the effectiveness of social robot (Paro) on people with dementia has shown inconsistent results. Previous studies have also found that different emotional attachments between human and Paro have shown different psychological effects for older adults. However, these conclusions still lack empirical research support. Therefore, the integrated project will conduct three sub-projects to examine the changes in biomedical, cognitive, and mental health of specific attachment older adults with dementia after receiving group-based Paro intervention. Study 1 will use a pilot randomized controlled trial to examine the effect of Paro intervention on oxytocin, dopamine and HRV variations for specific attachment older adults with dementia. A randomized controlled trial, single-blind, two parallel groups, and repeated measures design were used to examine the effects of Paro intervention on neurobiological changes for specific attachment older adults with dementia at before, during and after the intervention. A sample of 120 older adults with dementia who are 65 years or older living in long-term care will be invited. Older adults will be randomly assigned to two groups: experimental group or control group. The outcomes will be assessed based on the change of dopamine and HRV at baseline, 3rd week during the Paro intervention, the end of intervention (6th week), and the 1 month after the Paro intervention. Furthermore, the change of oxytocin will be assessed at two time points: baseline and the end of Paro intervention. Study 2 will focus on the 60 participants of the 2 experimental groups. A mixed method combined qualitative and quantitative research design will be used to explore the participating experience, group interaction, and its' association with mental health. Based on study 1 design, the outcomes of study 3 will be assessed based on the change of cognitive, executive functions, loneliness, depression, and well-being at the same points of study 1.

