To explore the interaction experience and its' relationship with the change of mental health undergoing group-based Paro intervention on people with dementia: Group process analysis

Abstract

Social robots have been validated as a therapeutic modality to provide stimuli to reduce the negative emotions and to improve the mental health for people with dementia. Different psychological effects for older adults those who had different emotional attachments styles between human and Paro had been found. However, these conclusions still lack empirical evidence and consistent results about the effectiveness of group-based social robot (Paro) on people with dementia.

Therefore, this integrated study will use a randomized controlled trial (RCT) to examine the process and outcomes of a weekly 6-session group-based Paro intervention. The association of group process and mental health for specific attachment older adults with dementia will be validated. A RCT, single-blind, four parallel groups, and repeated measures design were used to examine the effects of Paro intervention at before and after the intervention. Sixty older adults will be randomly assigned to two groups: experimental group or control group. In the subproject 2, we particularly focus on the 60 participants of the experimental group with dementia who are 65 years or older living in long-term care. A mixed method combined qualitative and quantitative research design will be used to explore the participating experience, group interaction, and its' association with mental health.

Thematic analysis will be conducted by the video-recorded, group process, memo and verbatim of 6 weekly 30-minute session Paro intervention after obtaining the inform consent of the participants. The group climate and satisfaction will be assessed at the end of 1st, 3rd, 6th session by group observers, and participants, respectively. The correlation will be examined between the group process with the change of loneliness and depression at pre- and post- intervention that conducted by subproject 3. We expect to assure and contrast the process and group effectiveness in this subproject. The study findings will provide empirical result to utilize the group-based Paro intervention for the older people with dementia. A strong evidence will be established to promote the alternative therapy into different attachment styles of dementia care, combining the

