This is a mixed method study that combined a qualitative and quasi-experimental design with two parallel groups. In the experimental groups, content analysis will be used to explore the group interaction experience with video-recorded and transcribe verbatim. A between-within subjects analysis of variance design will be used to assess the 6-session Paro intervention on the group process variables which include group climate and group satisfaction. Relationship between changes of group process and mental health by groups will be examined with a correlation analysis. Outcomes of interest measures will include group process at three time points: the first, third, and sixth session intervention; and mental health will be measured before the intervention and (T0) the end of intervention (6-session, T1).

The purpose of this study is to explore the relationship of group process and mental health undergoing group-based Paro intervention on older adults with dementia in LTC. The research design is shown in Table 1.

Table 1 Research design for exploring the group process and outcomes of group-based Paro intervention

Group	T0	Intervention / Group process	T1
Experiment group	O ₁	X (1 st , 3 rd , 6 th session)	O ₂

Note: T0 (before the intervention); T1 (after 6th session intervention); X (the group-based Paro intervention will be video-record, the group process will be analyzed by content analysis, and the group climate and satisfaction at session 1st, 3rd, and 6th will be assessed); O1, O2: Outcomes of measurement include the loneliness and depression assessment.

5. Sample size, Sampling, Settings, and Participants Recruitment

In the subproject 2, will focus on the participants in the experimental group (n=60). Contact has been made with the Directors of the LTC facilities who have expressed their interest in being involved in the study. Directors will invite older adults who meet the inclusion criteria to participate in this study.

The inclusion and exclusion criteria of elderly participants will be the same study 1.

6. Intervention

The Paro intervention will be the same study 1.

7. Outcome measures

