Differences between the pre and post-test in relation to outcome measures (loneliness and depression) will be used a mixed between-within subjects analysis of variance design to assess the immediate effects of the 6-week Paro intervention on mental health. The association of group process variables (group climate and satisfaction) and mental health will be examined for different attachment orientations of older adults living LTC facilities. A p value $< .05$ will be taken as the level of

statistical significance. The 95% confidence interval around the differences will be calculated.

III. Expectation Outcome

We expect to explore the group process and its' relationship with mental health (depression and loneliness) of 6-session group-based Paro intervention, and beneficial and hindering group experience of older adults with dementia.

IV. Ethical Considerations

Ethics approval for both phases of the study will be sought from Cheng-Kung University Human Research Ethics Committee and prior to the commencement of the study. Ethics approval for the study will also be sought from the participating LTC facilities in Taiwan prior to the commencement of the study. The researcher will inform the participants about the aims and objectives of the research study and what their participation will involve. Participants will be assured that (a) their participation will be on a voluntary basis and they are under no obligation to participate; and (b) they are free to withdraw from the study at any time without explanation, penalty or compromising their relationship with the LTC. A signed consent form will be sought from each participant. There are no foreseeable risks associated with participation in the intervention for participants.

All collected data will be stored electronically with password-protection to prevent unauthorised access to the data. All data and related documents will be kept in a key-locked cabinet for 5 years before being destroyed. Although demographic data will be requested, participants will remain anonymous. For quantitative data, all data will be de-identified at data entry and results will be reported in general terms. For qualitative data, the digital interview files will be deleted after transcription. Data will be de-identified with codes and content separated. Anonymity will be maintained via pseudonyms for direct interview quotes used in the reporting of findings.

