The aims of this study is to examine the effect of the Paro intervention on cognitive, executive functions and mental well-being for older people with dementia.

2. Objectives

- (6) To examine the effect of Paro intervention on cognitive and executive functions for older people with dementia.
- (7) To examine the effect of Paro intervention on depression for older people with dementia.
- (8) To examine the effect of Paro intervention on loneliness for older people with dementia.
- (9) To examine the effect of Paro intervention on mental well-being for older people with dementia.

3. Research design

This is a repeated measures study that is a randomized controlled trial, four parallel groups, and single-blind design. It is used to examine the effects of Paro intervention on cognition, executive functions, and mental well-being for older adults with dementia at before, during and after the intervention. A mixed between-within subjects analysis of variance design will be used to assess the immediate effects of the 6-week Paro intervention on cognitive, executive and three mental well-being related variables for different attachment orientations of older adults living LTC facilities. Outcomes of interest measures will include cognitive and executive functions, and depression, loneliness, and mental well-being at three time points: before the intervention (T0), middle of intervention (week-3, T1), the end of intervention (week-6, T2), and 1 month after the intervention (T2). Secondary outcome is interest in the impacts of the Paro intervention on psychological outcomes for different attachment style of older adults with dementia. The Revised Adult Attachment Scale Chinese version (RAAS-C) will be used to classify the attachment types of the elderly. A sub-group analysis will be conducted to further understand the changes in the physical and mental health of the elderly with different attachment types after receiving Paro intervention.

The purpose of this study is to examine the effect of Paro intervention on cognitive, executive, depression, loneliness, and mental well-being depression and loneliness for

older adults with dementia in LTC. The research design is shown in Table 1.

Table 1 Research design for Paro intervention

Group	T0	Intervention	T1	T2	T3
Experiment	O ₁	X	O ₂	O ₃	O ₄
Control	O ₁		O ₂	O ₃	O ₄

4. Sample size, Sampling, Settings, and Participants Recruitment

The same with study 1.

5. Intervention

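### Study 2's stated sample holds only the Paro arm, yet its pre-post ANOVA of loneliness and depression, with no named between-subject factor, is described as assessing the effects of Paro

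*Combined protocol and SAP*

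**What the plan says.** The statements that bear on this point are spread over three sub-studies.

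- **Study 2, sample (II.5):** "In the subproject 2, will focus on the participants in the experimental group (n=60"). The integrated abstract agrees that no controls are included: "Study 2 will focus on the 60 participants of the 2 experimental groups".
- **Study 2, research design (II.3):** "This is a mixed method study that combined a qualitative and quasi-experimental design with two parallel groups". Table 1 below it has a single row, the experiment group, and its note reads: "O1, O2: Outcomes of measurement include the loneliness and depression assessment".
- **Study 2, quantitative analysis (II.8(3)):** for loneliness and depression, the pre/post differences "will be used a mixed between-within subjects analysis of variance design to assess the immediate effects of the 6-week Paro intervention on mental health". Significance is taken at p < .05. Neither a between-subject factor nor a control comparison is named.
- **Study 2, abstract:** "A RCT, single-blind, four parallel groups, and repeated measures design were used to examine the effects of Paro intervention", and then "Sixty older adults will be randomly assigned to two groups: experimental group or control group". The same paragraph goes on to say that the subproject concentrates on the 60 people in the experimental group.
- **Study 1, sample size (II.4), which Study 3 adopts:** 120 participants, 60 per group.
- **Study 3:** one objective is "To examine the effect of Paro intervention on depression for older people with dementia", and a parallel one covers loneliness. Its Table 1 has experiment and control rows, and its Table 2 schedules the UCLA and GDS-SF at baseline, week 3, week 6 and follow-up. The model sentence in its data analysis section (I.8) tests arms on pre-post differences, but the outcomes it lists are oxytocin, dopamine and HRV.

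**The concern.** A mixed between-within ANOVA estimates a treatment effect only if treatment is the between-subject factor. In the sample and table that Study 2 states, everyone receives Paro, so no such factor exists. What remains is change over six weeks in treated people, and the plan's wording would let that change be reported as an effect of Paro.

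The same two scales, in the same Paro participants over the same interval, also enter Study 3 beside 60 randomised controls. The project could therefore report two results for the effect of Paro on mood, only one of them controlled, with nothing in the plan to say which governs. Study 2's statement of expected contribution speaks of examining the intervention's effect and of strong evidence, so a significant uncontrolled change could be published as efficacy even if the randomised contrast shows nothing.

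**Working it through.** **1. What each analysis estimates.** Let c be the six-week change that would occur in either arm without Paro, and e the effect of Paro.

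- Mean change, Paro arm: c + e.
- Mean change, control arm: c.
- Study 2's time term (Paro arm only) estimates c + e.
- The Study 3 contrast estimates (c + e) − c = e.

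Adding a within-arm factor such as therapy group or attachment type does not help. The time term still estimates c + e averaged over levels, and the factor-by-time term compares levels of that factor, all of them treated.

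**2. Plan figure to reproduce.** None bears on this point. The 120 is given without effect size, SD, power or dropout.

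**3. How often the one-arm test rejects when e = 0.** Inputs: n = 60 (Study 2, II.5) and α = 0.05 (II.8(3)), with two-sided testing assumed because the plan does not say. The documents give neither a background change nor a pre-post correlation r, so both are assumed: a shift of 0.1 to 0.3 baseline SD, and r of 0.5 to 0.8.

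Formulas: d_z = shift / √(2(1 − r)); noncentrality = d_z × √60; reject when |t| > 2.001 on 59 df.

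Example: shift 0.2 and r = 0.7 give d_z = 0.2 / √0.6 = 0.258 and noncentrality 0.258 × 7.746 = 2.00, so the rejection probability is 0.50.

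| Shift (SD) | r = 0.5 | r = 0.7 | r = 0.8 |
|---|---|---|---|
| 0.1 | 12% | 17% | 23% |
| 0.2 | 33% | 50% | 67% |
| 0.3 | 63% | 84% | 95% |

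With no background change the rate is 5%.

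**4. Does an extra between factor rescue it?** A simulation of 20,000 runs used an assumed three-level factor, 20 people per level, inside the Paro arm. With a background change of 0.1, 0.2 and 0.3 SD of the change score, the time term rejected about 12%, 33% and 63% of the time, the same as the paired test at r = 0.5, where the two SDs coincide. The factor-by-time term stayed near 5%, but it does not estimate a Paro effect.

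**5. The randomised contrast.** With independent participants and 60 vs 60, the simulated rejection rate was 4.8% to 5.0% for shared changes of 0 to 0.5 SD of the change score. Independence is itself an assumption, because Paro is given in groups of 6 to 8. Take ten Paro groups of 6 and unclustered controls. The variance of the Paro mean is multiplied by 1 + 5 × ICC, which is 1.25, 1.5 and 2.0 at assumed ICCs of 0.05, 0.1 and 0.2. The variance of the difference is then multiplied by 1.125, 1.25 and 1.5. An ordinary two-sample test rejects about 6.5%, 8% and 11% of the time (simulated, no true effect). The contrast is not biased by a shared change, but its nominal level needs an allowance for clustering.

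**The case against.** The best defence is that II.8(3) never says the ANOVA is run in the Paro arm alone. A mixed design implies a between factor, II.3 speaks of two parallel groups, Study 2's objectives 2 to 4 are to be examined by groups, and the sentence closely resembles the Study 3 one, where controls are present. This stands in part. A reader might infer that the plan has knowingly chosen a one-arm efficacy analysis, and the documents do not establish that. They leave the factor unnamed and describe the groups inconsistently. But if controls were intended, the sample statement and the one-row table are wrong; if not, the description of the result as an effect is wrong. Either way the text needs correcting.

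Second, a reader might infer from the Study 2 abstract that it defines a rival trial of 60 people, 30 per arm, with correspondingly lower power. The documents do not support that. The RCT text can be read as describing the parent project with Study 2 nested in it, the same paragraph puts 60 in the experimental group, and elsewhere the total is 120. The word Sixty is an isolated inconsistency.

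Third, the consequence is contained. Study 2's primary outcome is group experience. Its aim and objectives concern experience, climate, satisfaction and their relationship with outcomes, and its abstract assigns the loneliness and depression assessments to subproject 3. This stands and limits the severity.

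Fourth, the size of the background change is assumed. This also stands. Retest, season or ordinary facility activity are possible sources, but no section quantifies them. Regression to the mean is a weak argument here, because eligibility does not select on mood scores.

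**Conclusion.** The point holds as a mismatch between Study 2's stated sample and the label on its analysis. With only Paro participants, no available factor isolates the effect of Paro, so the pre-post result for loneliness and depression should not carry that name. This conclusion follows from the design and needs no numerical assumption.

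The false-positive rate is conditional: 12% to 95% under the assumed shifts and correlations, 50% at 0.2 SD and r = 0.7, and 5% if there is no background change. The range illustrates sensitivity and is not a forecast. Nor should a reader infer that the Study 3 test is assured of its 5% level; that also depends on how clustering by Paro group is handled.

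The correction is worth making but does not threaten the trial's main comparison: Study 2 is chiefly a process study, and the controlled data on both scales are already planned.

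**What to change.** 1. **Study 2, II.8(3):** stop describing the pre-post result as the effect of Paro. Call it descriptive within-arm change, used as input to the association with group process. If a subgroup-by-time analysis is kept, name its between-subject factor and say that it compares subgroups of treated people.
2. **Governing contrast:** state that the effect of Paro on loneliness and depression is the Paro-versus-control contrast in change from Study 3, 60 vs 60.
3. **Study 3, I.8:** name loneliness and depression in the model sentence, which now lists only oxytocin, dopamine and HRV, and say how clustering by Paro group is allowed for.
4. **Study 2, abstract:** reconcile Sixty with 120 in total, 60 per group.
5. **Study 2, II.3:** reconcile the two parallel groups with the one-row table.

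The cost is a few sentences. No new data are needed, since Study 3 already schedules both scales in both arms, and the group-process aim is untouched. The downside is that Study 2 no longer reports its own effect p-value.

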Participants in the experimental group will receive a group (6-8 people as a group), facilitated, and 30-minute weekly session Paro intervention for 6 weeks. The control group will receive care as usual activities, such as painting, drawing, and craft, which are provided by each facility.

6. Procedure of interaction records

Participants in experimental groups will receive a group, facilitated, 30-minute weekly session of Paro intervention. A trained research assistant (RA) will give the Paro to the participants at the start of each session, repeating the same introductory script each time. The RA facilitate the participant interact with the Paro during the intervention, after 30 minutes RA will use the same ending script to end the session and goodbye to participants.

7. Outcome measures

The process and outcome of measurement will be blinded and assessed by another RA at four time points: baseline (T0), Week 3(T1), Week 6 (T2), and 1 month after the end of intervention(T3). The primary outcomes are global cognitive function and executive functions. The Mini-Mental State Examination (MMSE) will be used to assess participants' global cognitive function. The executive functions include two components such as working memory (WM) and response inhibition, which will use computerized tasks to assess the changes of executive functions for order adults before and after intervention. Working memory will be assessed using verbal WM and visuo-spatial WM tasks. Response inhibition will be assessed employing color word stroop

(CWS), stop signal (SS), and go/no-go (GNO) tasks. The secondary outcome measures are loneliness (UCLA version-3), Depression (GDS-SF), and Mental well-being (WEMWBS).

Table 2 Measurement time points and measurements

Instrument	Week-0 (T0)	Week-3 (T1)	Week-6 (T2)	Follow- up (T3)
Demographics/disease information	√			
RAAS-C	√			
Outcome measure				
-MMSE	√	√	√	√
-Executive Functions	√	√	√	√
-Loneliness (UCLA)	√	√	√	√
-Depression(GDS-SF)	√	√	√	√
-Mental well-being (WEMWBS)	√	√	√	√

Note. √, collect data; MMSE; executive function; UCLA, the University of California Los Angeles Loneliness Scale version 3; GDS-SF, Geriatric Depression Scale - Short Form; WEMWBS, Warwick-Edinburgh Mental Well-being Scale.

(1) Demographic data

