To probing the change of the markers, a series of paired sample t-test will be used for each group. To testing the research hypothesis, a mixed designed generalized linear model (GLM) will be employed to test the effects of arms on the differences between the pre and post-test in relation to outcome measures, including oxytocin level, dopamine and HRV changes for different attachment orientations of older adults living LTC facilities. In order to increase precision in estimating the effect of interest, the possible confounding effects of the covariates, such as age, education, etc, will be used to take into account as covariate in the model. The effect size will be calculate to show the magnitude and direction of the effect in the attachment-specific group relative to the control for each outcome variable. In order to identify the optimal duration of clinical application for this intervention, a trend analysis will be conducted. Exploratory additional analysis will be conducted to test the interaction between intervention, and potential biomarker on clinical evaluation. A p value $< .05$ will be taken as the level of statistical significance. The 95% confidence interval around the differences will be calculated.

II. Expectation Outcome

We expect to identify positive effect of Paro intervention on cognitive, executive functions, depression, loneliness, and mental well-being for older adults with dementia.

III. Ethical Considerations

Ethics approval for both phases of the study will be sought from Cheng-Kung University Human Research Ethics Committee and prior to the commencement of the study. Ethics approval for the study will also be sought from the participating LTC facilities in Taiwan prior to the commencement of the study. The researcher will inform the participants about the aims and objectives of the research study and what their participation will involve. Participants will be assured that (a) their participation will be on a voluntary basis and they are under no obligation to participate; and (b) they are free to withdraw from the study at any time without explanation, penalty or compromising their relationship with the LTC. A signed consent form will be sought from each participant. There are no foreseeable risks associated with participation in the intervention for participants.

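### For the primary outcomes measured at four visits, the plan fixes no primary time point, visit set or tested term, and a group-by-time test would not isolate the week-6 effect

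*Combined protocol and SAP*

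**What the plan says.** **Mixed ANOVA.** Study 1 (II.3 Research design), the Study 3 abstract and Study 3 (I.3 Research design) share a sentence: "A mixed between-within subjects analysis of variance design will be used to assess the immediate effects of the 6-week Paro intervention". It continues "on cognitive, executive and three mental well-being related variables for different attachment orientations of older adults living LTC facilities". None of the three places says which visits enter the model, or whether the test is the group effect, the interaction or a contrast.

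**GLM.** Study 3 (I.8 Data analysis), under the aim of testing the research hypothesis, says "a mixed designed generalized linear model (GLM) will be employed to test the effects of arms on the differences between the pre and post-test". The outcomes it names are those "including oxytocin level, dopamine and HRV changes for different attachment orientations of older adults living LTC facilities". The post-test visit is not defined. Study 1 has no data analysis section of its own.

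**Study 2** (II.8(3) Quantitative data analysis) applies the mixed ANOVA to a pre-post comparison: "Differences between the pre and post-test in relation to outcome measures (loneliness and depression) will be used a mixed between-within subjects analysis".

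**Visits.** The two design sections announce three time points, list four, and end with "the end of intervention (week-6, T2), and 1 month after the intervention (T2". The outcome sections of both studies (Study 1 II.8, Study 3 I.7) give four time points: "baseline (T0), Week 3(T1), Week 6 (T2), and 1 month after the end of intervention(T3". Both Table 1s and both Table 2s have separate T2 and T3 columns. The note to Study 1's Table 1 places the visits at baseline and weeks 3, 6 and 10.

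**Primary outcomes.** Study 1 names oxytocin, FTT and HRV. Study 3 names global cognition (MMSE) and executive functions. All have four visits except oxytocin, which has baseline and end of intervention only. Neither study names a primary visit.

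**The concern.** The stated target is the effect of the completed six-week programme. A reader cannot tell which number will answer that question for FTT, HRV, MMSE or executive functions: an interaction over three or four visits, a group main effect, or a change score to one of three later visits. These answer different questions and can disagree.

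Two things follow. First, a group-by-time test responds to a difference in change at any included visit, so a passing week-3 difference or a late week-10 difference could be reported as the programme's immediate effect. Second, the model and the visit could be chosen after the data are seen, which raises the false-positive rate.

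The outcome lists add to the doubt. Study 1's ANOVA sentence names cognition and well-being, which are Study 3's outcomes. Study 3's GLM sentence names oxytocin, dopamine and HRV, which are Study 1's. The lists look misplaced, and read literally they leave MMSE and executive functions with only the ANOVA, and FTT and HRV with only the undefined pre-post test.

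**Working it through.** The plan gives no power calculation, SD, effect size or within-person correlation, so there is no figure of its own to reproduce.

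**Inputs from the documents:** n = 60 per arm; visits at weeks 0, 3, 6 and 10; significance level 0.05 (sidedness not stated, two-sided taken).

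**Assumptions not in the documents:** compound symmetry; correlation ρ from 0.5 to 0.8; standardised effects of 0.3 or 0.5 SD; no dropout; no clustering by facility or group.

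**1. Group-by-time term.** With arm difference d_t at visit t and k visits, the noncentrality is λ = (n/2) Σ(d_t − d̄)² / (1 − ρ), on k − 1 and (2n − 2)(k − 1) df.

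Four visits, 0.5 SD at week 10 only: d̄ = 0.125; Σ = 3 × 0.125² + 0.375² = 0.1875; λ = 30 × 0.1875/(1 − ρ) = 5.625/(1 − ρ), on 3 and 354 df. At 0.3 SD: Σ = 0.0675 and λ = 2.025/(1 − ρ). An effect at week 3 only gives the same values, because Σ does not depend on which visit differs.

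Three visits (weeks 0, 3, 6), 0.5 SD at week 3 only: Σ = 2 × 0.1667² + 0.3333² = 0.1667; λ = 5/(1 − ρ), on 2 and 236 df.

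**2. Week-6 contrast.** The change-score SE in SD units is √(2(1 − ρ) × 2/60), on 118 df. With no week-6 effect it rejects 5% of the time, whatever happens at weeks 3 and 10.

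| Scenario | ρ = 0.5 | ρ = 0.7 | ρ = 0.8 |
|---|---|---|---|
| Four-visit interaction, 0.5 SD at week 10 only | 80.9% | 96.4% | 99.7% |
| Four-visit interaction, 0.3 SD at week 10 only | 35.9% | 56.7% | 76.2% |
| Three-visit interaction, 0.5 SD at week 3 only | 81.0% | 96.2% | 99.6% |
| Three-visit interaction, week-10-only effect | 5% | 5% | 5% |
| Week-6 contrast in any row above | 5% | 5% | 5% |
| Week-6 contrast, true 0.5 SD at week 6 | 77.5% | 93.9% | 99.0% |

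The group main effect over four visits rejects in 11–14% of trials for a 0.5 SD effect at a single visit other than week 6. In 20,000 simulated trials with 0.5 SD at week 10 only, the four-visit interaction was significant while the week-6 change was not in 76% (ρ = 0.5) and 91% (ρ = 0.7).

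**3. Power for a real week-6 effect.** This depends on the profile over weeks 3, 6 and 10:
- 0.25/0.5/0.25 SD (builds and fades): four-visit interaction 62–96%, week-6 contrast 78–99%.
- 0.25/0.5/0.5 SD (builds and holds): 77.0/94.8/99.4% against 77.5/93.9/99.0% at ρ = 0.5/0.7/0.8. There is no material loss.

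**4. Choice after seeing the data, no true effect.** Changes to two later visits from a shared baseline correlate 0.5 under compound symmetry. The chance of at least one p < 0.05 per outcome is:
- 9.1% if the post-test visit may be week 6 or week 10;
- 12.5% if it may be any of the three visits;
- 8.1–8.4% if either the four-visit interaction or the week-6 change may be called positive.

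**5. Oxytocin.** With two visits, the interaction and the pre-post comparison are the same test, so the problem does not arise.

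**The case against.** Much can be said for the plan, and several stronger readings do not survive it.

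- *A reader might infer that the immediate effect is assigned to both tests.* It is not. That word goes only with the ANOVA; the GLM is described as the test of the research hypothesis.
- *A reader might infer two conflicting tests of one primary outcome.* The named outcomes do not overlap. The GLM's list is introduced as inclusive and sits in Study 3's section, so overlap is possible, but it is not stated. Study 2's use of the ANOVA for a pre-post comparison suggests one mixed-design model may have been described twice.
- *A reader might infer a four-visit omnibus test.* That comes from the schedule; the text does not say so. If the model stops at week 6, a week-10-only effect does no harm. A week-3-only effect still does.
- *A reader might infer that the repeated T2 label leaves the visit unknown.* The outcome sections and tables settle it: T2 is week 6 and T3 is one month later. It is a slip.
- The phrase about immediate effects points naturally to the end of the programme, and Study 2 measures its outcome after the sixth session. Week 3 is called the middle of the intervention, so the 12.5% figure takes a generous view of what counts as post-test; 9.1% is the narrower one.
- The trial is described as a pilot, and an omnibus test followed by contrasts is legitimate if specified.

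These points narrow the claim. They do not supply the missing primary visit, visit set or tested term.

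**Conclusion.** The gap is real and should be fixed. For FTT, HRV, MMSE and executive functions, no section fixes the primary time point, the visits in the model or the term tested, and the outcome lists appear misplaced between Studies 1 and 3. Read through its group-by-time term, the ANOVA does not isolate the effect it is said to assess.

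The direction of that result needs no assumption about effect size or correlation. The percentages do, and they are illustrative: the high rejection rates require an effect at one visit and none at week 6. The evidence does not show that the ANOVA is generally underpowered, since a sustained effect costs it essentially nothing. Nor does it show that the two analyses must conflict. The excess false-positive risk, about 9% to 12.5% against a nominal 5%, is per outcome and arises only if the visit is chosen after the data are seen. Oxytocin is unaffected.

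**What to change.** 1. For each primary outcome measured at four visits in Studies 1 and 3, name one primary analysis: the Paro-minus-control difference in change from baseline to week 6, taken from a repeated-measures model with arm-by-visit terms.
2. Make the week-3 and week-10 contrasts and the omnibus interaction secondary.
3. List each study's own outcomes under this analysis: FTT and HRV for Study 1, MMSE and executive functions for Study 3. Oxytocin keeps its baseline-to-week-6 comparison.
4. As a minor correction in both Research design sections, change the second T2 to T3 and the count of three time points to four.

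The cost is wording in the protocol and analysis plan. No visit, measurement or participant is added. The downside is that an effect confined to week 3 or week 10 becomes a secondary finding.
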